2.0 CLINICAL PROTOCOL SYNOPSIS

Name of Sponsor:	Urgen N.A., Inc.
Name of Product:	URG101
Protocol Title:	A Phase 2a, Randomized, Double-Blind, Placebo-Controlled Multi-Center Single Dose Study to Evaluate the Safety and Effectiveness of URG101 Compared with the Individual Components Lidocaine and Heparin in Subjects with Interstitial Cystitis/Bladder Pain Syndrome (Protocol URG101-105, the ENGAGE-24 Study)
Clinical Phase	2a
Objectives:	
Primary Objective:
 
 1. To evaluate the change in sum of bladder pain intensity differences from baseline to 12 hours (SPID-12) after administration of URG101 compared with the SPID-12 after administration of lidocaine alone, heparin alone, and placebo as determined by using the 11-point NRS for bladder pain. 
Secondary Objectives:
 
 1. To evaluate the change in bladder pain from baseline to 24 hours, using the sum of pain intensity differences (SPID-24) at defined time points, after administration of intravesical URG101 compared with alkalinized Lidocaine Hydrochloride Injection (20 mg/mL) alone, alkalinized Heparin Sodium Injection (5,000 USPU/mL) alone, and placebo (██████████) 2. To evaluate the change in urgency from baseline to 12 and 24 hours, using the sum of urgency intensity differences (SUID) at defined time points, after administration of URG101 compared with alkalinized Lidocaine Hydrochloride Injection (20 mg/mL) alone, alkalinized Heparin Sodium Injection (5,000 USPU/mL) alone, and placebo (██████████) 3. To evaluate the absolute and percentage change in bladder pain and urgency intensity differences at 1, 12, and 24 hours after administration of URG101 compared with alkalinized Lidocaine Hydrochloride Injection USP (20 mg/mL) alone, alkalinized Heparin Sodium Injection USP (5,000 USPU/mL) alone, and placebo (██████████) 4. To evaluate the improvement of symptoms after treatment with URG101, measured using the Patient Global Assessment (question number 3) compared with alkalinized Lidocaine Hydrochloride Injection (20 mg/mL) alone, alkalinized Heparin Sodium Injection (5,000 USPU/mL) alone, and placebo (██████████) at 1, 12, and 24 hours after treatment 5. To evaluate the time to first administration of rescue medication for pain after treatment with URG101 compared to alkalinized Lidocaine Hydrochloride Injection (20 mg/mL) alone, alkalinized Heparin Sodium Injection (5,000 USPU/mL) alone, and placebo (██████████) 6. To investigate the relationship of plasma lidocaine concentrations at 1 hour after study drug administration to bladder pain and urgency at 1 hour, and from baseline to 12 and 24 hours, using the sum of pain and urgency intensity differences at defined time points, after administration of URG101 compared with alkalinized Lidocaine Hydrochloride Injection (20 mg/mL) alone, alkalinized Heparin Sodium Injection (5,000 USPU/mL) alone, and placebo (██████████) 7. To evaluate the safety and tolerability of intravesical administration of URG101
Study Design:	This is a Phase 2a, prospective, randomized, double-blind, placebo-controlled,

CLINICAL PROTOCOL SYNOPSIS (continued)

multicenter, single-dose, pharmacokinetic study designed to test the efficacy and safety of the combination product (URG101) versus its alkalized individual components (Heparin Sodium and Lidocaine Hydrochloride) and placebo [REDACTED]. A maximum of 300 subjects will be enrolled in Study URG101-105.

In this study, alkalized Lidocaine Hydrochloride Injection (20 mg/mL) and alkalized Heparin Sodium Injection (5,000 USPU/mL) will be subsequently referred to by the drug names Lidocaine and Heparin.

Eligible subjects exhibiting interstitial cystitis symptoms who have signed informed consent, will be screened and provisionally enrolled for intravesical treatment. Treatment may occur on the day of the Screening Visit (Visit 1) or any following day up to 1 week (Baseline and Drug Administration Visit 1a). If drug administration occurs on same day as screening then all assessments in Visit 1 and Visit 1a will be combined. If screening (V1), and baseline and drug administration (V1a) do not occur on same day, urine pregnancy test for women of childbearing potential and urine screen for drugs of abuse must be performed at both visits (V1 and V1a). Confirmation of symptom severity must be obtained before randomization: minimum pain score of 5 on the 11-point numerical rating scale [NRS] at Screening and 15 minutes (\pm 5 minutes) after voiding prior to study drug administration. Subjects will become fully enrolled upon receipt of acceptable qualifying laboratory evaluations (obtained via dipstick) and clinical assessments obtained before randomization.

At the Screening Visit (V1), the following will be completed: medical history and demographics; medication history; the Pelvic Pain and Urgency/Frequency (PUF) questionnaire; 11-point NRS for bladder pain and urgency; a physical examination, including a pelvic examination to confirm lower urinary tract tenderness; vital signs; blood and urine samples for safety laboratory assessments (including urine hematuria analysis); urine pregnancy test for women of childbearing potential; urine screen for drugs of abuse; and concomitant medications. (Note: results from a pelvic examination performed within 7 days prior to the Screening Visit (V1) may replace a V1 pelvic examination.)

[REDACTED]

On the day of study drug administration (V1a), subjects will be randomized (2:1:2:1); URG101:placebo:lidocaine:heparin) and will receive a single administration of one of four intravesical treatments in a blinded fashion, based on random assignment:

1. Combination product, URG101 (buffered heparin-lidocaine)
2. Placebo: [REDACTED]
3. Lidocaine: [REDACTED]
4. Heparin: [REDACTED]

Subjects will be monitored for 2 hours in the clinic after study drug administration.

CLINICAL PROTOCOL SYNOPSIS (continued)

	
Subjects will maintain a urination log and symptom diary after discharge and will return to the clinic the following day to complete the in-clinic study procedures and collection of the study diary.
 
The following will be completed according to the schedule of assessments over a 24-hour period after study drug administration: the 11-point NRS for bladder pain and urgency; the PORIS questionnaire; vital signs assessments; blood samples for safety laboratory assessments, i.e. blood coagulation (prothrombin time [INR] and activated partial thromboplastin time [aPTT]), and plasma lidocaine concentrations; adverse events; and concomitant medication assessments.
 
Subjects will be contacted within 48 to 72 hours after the last study treatment to follow-up on any ongoing adverse events after the last clinic visit.
 
The clinical study will plan to randomize 180 subjects. After 90 (50%) subjects have been enrolled and treated, the IDMC will examine the conditional power and determine if a modification to the sample size is required to yield an overall power of 90%. An adjustment to the type 1 error rate will not be necessary if the conditional power is >39% at the interim assessment.
 
The IDMC will consist of 3 members: 1 physician expert in IC/BPS, 1 expert in clinical development, and a biostatistician. None of the IDMC members will be associated with study personnel; all communication between the IDMC and study personnel will be pre-defined and governed by the IDMC charter. The IDMC will have access to unblinded pain scores to perform their ranking of the pain endpoints and for assessment of conditional power.

Estimated Number of Subjects:	A target of 180 subjects subject to adjustment by the IDMC. A maximum of 300 subjects will be enrolled in Study URG101-105.
Number of Study Sites:	Up to 30 sites in the United States and Canada
Subject Population:	Adult subjects, aged \geq 18 years, with Interstitial Cystitis who have moderate-to-severe symptoms of pain and/or urgency of bladder origin for at least 9 months, not currently taking narcotic pain medications, meeting the minimum screening scores.
Study Drug, Dose, Formulation, Method of Administration:	
URG101: buffered lidocaine and heparin, instillation via urethral catheter. URG101 treatment comprises the following:
 
 • 18 mL containing Heparin Sodium [REDACTED] 
Placebo treatment comprises the following:
 
 • 18 mL [REDACTED] 
Heparin treatment comprises the following:
 
 • 12 mL Heparin Sodium [REDACTED], plus 6 mL 3X [REDACTED] buffer [REDACTED] 
Alkalinized Lidocaine treatment comprises the following:
 
 • 12 mL Lidocaine HCl ([REDACTED]), plus 6 mL 3X [REDACTED] buffer [REDACTED]
Criteria for Evaluation:	
Primary Endpoint:
 
 1. A measure of the sum of bladder pain intensity differences from baseline to

CLINICAL PROTOCOL SYNOPSIS (continued)

	
12 hours (SPID-12) after administration of URG101 compared with the SPID-12 after administration of lidocaine alone, heparin alone, and placebo as determined by using the 11-point NRS for bladder pain
 
Secondary Endpoints:
 
 1. The sum of bladder pain intensity differences from baseline to 24 hours (SPID-24) after administration of URG101 compared with lidocaine alone, heparin alone, and placebo as determined by using the 11-point bladder pain NRS 2. The sum of urgency intensity differences from baseline to 12 and 24 hours (SUID-12 and SUID-24) after administration of URG101 compared with lidocaine alone, heparin alone, and placebo using the 11-point urgency NRS 3. Absolute and percentage change in bladder pain from baseline to 1, 12, and 24 hours after administration of URG101 compared with lidocaine alone, heparin alone, and placebo as determined by using the 11-point NRS for bladder pain 4. Absolute and percentage change in urgency intensity from baseline to 1, 12, and 24 hours after administration of URG101 compared with lidocaine alone, heparin alone, and placebo using the 11-point urgency NRS 5. Patient Global Assessment: Comparison of the percentage of subjects achieving $\geq 50\%$ improvement in the PORIS questionnaire(Question 3), from baseline to 1, 12, and 24 hours after administration of URG101, lidocaine alone, heparin alone, and placebo 6. Time to first administration of rescue medication for pain after treatment with URG101 compared to alkalinized Lidocaine Hydrochloride Injection (20 mg/mL) alone, alkalinized Heparin Sodium Injection (5,000 USPU/mL) alone, and placebo [REDACTED]) 7. To evaluate the safety and tolerability of intravesical administration of URG101
	
Pharmacokinetic Endpoints:
 
 1. Comparison of plasma lidocaine concentrations at 1 hour post treatment with absolute and percentage change in pain using the 11-point NRS for bladder pain at 1, 12 and 24 hours after administration of URG101, lidocaine alone, heparin alone, and placebo 2. Comparison of plasma lidocaine concentrations at 1 hour post treatment with absolute and percentage change in urgency using the 11-point NRS for urgency, at 1, 12 and 24 hours after administration of URG101, lidocaine alone, heparin alone, and placebo 3. Comparison of plasma lidocaine concentrations at 1 hour post treatment with the sum of bladder pain intensity differences from baseline to 12 and 24 hours (SPID-12 and SPID-24) after administration of URG101 compared with lidocaine alone, heparin alone, and placebo as determined by using the 11-point bladder pain NRS 4. Comparison of plasma lidocaine concentrations at 1 hour post treatment with the sum of urgency intensity differences from baseline to 12 and 24 hours (SUID-12 and SUID-24) after administration of URG101 compared with lidocaine alone, heparin alone, and placebo as determined by using the 11-point urgency NRS 
Safety Endpoints:
 
 1. Change from baseline in INR at 1 hour after study drug administration

CLINICAL PROTOCOL SYNOPSIS (continued)

	
2. Change from baseline in aPTT at the 1-hour post-study-drug time point 3. Adverse events
 
Pharmacokinetics: Samples for peak plasma lidocaine concentrations will be collected at baseline and at 1 hour after study drug administration.
 
Efficacy:
 
 • 11-point (i.e., 0 to 10) NRS bladder pain (numerical rating scale) • 11-point (i.e., 0 to 10) NRS urge (urgency intensity) to urinate (numerical rating scale) • PORIS questionnaire 
Safety: The following safety parameters will be evaluated:
 
 • Clinical laboratory tests • Vital sign measurements • Physical examination • Incidence of adverse events, serious adverse events • INR and aPTT 
Follow-up will occur for subjects with clinically significant, study drug-related abnormalities at the conclusion of the study termination visit, based on the investigators discretion.

Statistical Methods:	
Sample Size Estimate Sample size estimates were based on a pilot trial of heparin-lidocaine versus lidocaine alone and a prior two-arm study of URG101 versus placebo. The primary efficacy endpoint is SPID-12. The sample size calculation is based on a one-way analysis of variance, comparing SPID-12 from four treatment groups. A target sample size of 180 subjects to be allocated unequally among the four treatment groups as follows: URG101:placebo:lidocaine: heparin at 2:1:2:1 (60 subjects per group and 30 subjects per group). This sample size is sufficient to achieve 90% power to detect a difference between the URG101 and lidocaine groups assuming a treatment effect size of 0.60. The study will also have 90% power to detect a difference between the URG101 and each of the placebo and heparin groups assuming an effect size for these comparisons of 0.75. Once 90 subjects have been enrolled, a blinded interim analysis will take place; and, if required, the number of subjects for the study increased to a maximum of 300 subjects.
 
Description of Analysis Sets: All analyses of the efficacy of URG101 will be performed on the ITT set, which will include all randomized subjects from the investigative phase of the study who receive study drug. These efficacy analyses will compare the treatment groups on the basis of randomized treatment, regardless of the treatment actually received. Primary efficacy and key secondary efficacy analyses will also be conducted on a per protocol set, which will include all subjects in the ITT set who sufficiently comply with the protocol.
 
Safety analyses will be based on the safety analysis set which will include all subjects who receive at least one dose of study drug and have at least one post dose safety assessment in both phases of the study. Safety summaries will be produced based on study treatment actually received.

CLINICAL PROTOCOL SYNOPSIS (continued)

	
Primary Efficacy Determination: The primary efficacy endpoint will be compared between the URG101 and the lidocaine, heparin, and placebo groups using an analysis of covariance model which will include factors for treatment and baseline pain values. Pairwise comparisons of least squares means between URG101 and each of the other treatment arms will be performed. If the p-value associated with these comparisons is < 0.05 in favor of URG101, the primary aim of the trial will be confirmed.
 
Missing data for efficacy values will be imputed by the last observation carried forward method.
 
Secondary Efficacy Determinations: Analyses of secondary endpoints relating to changes in the NRSs for pain and urgency will be performed using analysis of covariance models similar to that used for the primary efficacy endpoint. Nonparametric methodology in exploratory analyses may be used to supplement the parametric analyses.
 
Treatment group comparisons relative to improvement on the PORIS questionnaire, (Question 3), will be made with standard contingency table techniques.
 
Pharmacokinetic Determinations: A comparison of pain and urgency assessments as measured by 11-point NRS to plasma lidocaine concentrations at 1 hour after study drug administration will be made for the PK set.

	
Safety Determinations: All safety analyses will be performed on the safety analysis set.
 
The change in INR and aPTT at baseline and 1 hour will be compared for the various treatment groups using descriptive statistics.
 
Other Determinations: Demographic and disposition data, randomization, drug administration, medical history, prior and concomitant medications, adverse events, clinical laboratory measurements, vital signs, physical examination findings, and all other safety data will be listed by subject and time point. Descriptive statistics will be tabulated for change from baseline in the vital signs. In addition to clinical and laboratory assessments, subject safety will be monitored by recording adverse events and serious adverse events throughout the study. Any pregnancy that occurs during the study will be promptly reported to the sponsor, but will not be considered a serious adverse event. Treatment-emergent adverse events will be summarized by type, frequency, severity, relationship to study drug, and number of subjects per treatment. Adverse events will be coded according to the Medical Dictionary for Regulatory Activities.

Duration of Treatment:	Each study subject will receive a single dose of URG101, placebo ([REDACTED]), alkalinized Lidocaine, or alkalinized Heparin by random assignment. The randomization ratio will be 2:1:2:1, respectively.

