- the PORIS questionnaire at 1 hour (\pm 15 minutes) after study drug administration;
- vital signs measurements (i.e., systolic and diastolic blood pressure, heart rate, respiratory rate, and oral body temperature) will be obtained at 1 hour (\pm 15 minutes) after study drug administration;
- concomitant medications;
- and adverse events.

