9.1.3 Home Assessment

After instructions, the subjects will be discharged from the clinic and reminded to

return the next day for the optional 24 hour Follow-up Visit. However, return of subject diaries including 24 hour assessments are mandatory. All assessments and their respective timing are provided in Table 4. The following assessments will occur >2 hours post study drug administration but before 24-hour Follow-up Visit (V2):

- 11-point NRS for bladder pain and urgency at 4 hours (\pm 30 minutes), 6 hours (\pm 30 minutes), 8 hours (\pm 30 minutes), 10 hours (\pm 30 minutes), and 12 hours (\pm 30 minutes) (only during times the subject is awake);
- the PORIS questionnaire at 12 hours after study drug administration or before the subject goes to bed for the evening;
- urination log;
- adverse event reporting;
- and concomitant medications.

9.1.4 24-Hour Follow-up Visit (Visit 2; Optional)

Approximately 24 hours after study drug administration, the subjects will return to the clinic for end-of-study assessments. The following assessments will occur:

- subject's diary collection is mandatory to evaluate the efficacy of URG101;
- 11-point NRS for bladder pain and urgency at 24 hours (\pm 2 hours) is mandatory to be completed and returned;
- the PORIS questionnaire at 24 hours (\pm 2 hours) after study drug administration is mandatory to be completed and returned;
- vital signs measurements at 24 hours (\pm 2 hours) after study drug administration (i.e., systolic and diastolic blood pressure, heart rate, respiratory rate, and oral body temperature) is optional;
- and recording of any adverse events or concomitant medications is mandatory to be collected and returned for safety evaluation.

In the opinion of the Investigator, if the subject appears responsible to perform the 24 hour assessments, correctly fill out the diary for all of the at home assessments, and the Investigator and the subject have made acceptable arrangements for the return of the diaries, answering of any follow up questions, and for the subject's treatment and care after 24 hours, then Visit 2 may be considered an optional protocol visit to the clinic.

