9.5.2.2 Patient Overall Rating of Improvement of Symptoms Questionnaire

The PORIS questionnaire is provided in [Appendix 5](#). It comprises three questions that ask the subject to report the overall change in pain and urgency *now* as compared with *before* study drug administration. The choices are the same for each symptom: worse, no better (0% improvement), slightly improved (25% improvement), moderately improved (50% improvement), greatly improved (75% improvement), and symptoms gone (100% improvement). The PORIS questionnaire will be explained to each subject by the investigator or designee prior to the subject completing the questionnaire. A guideline script for the PORIS questionnaire is provided in [Appendix 6](#).

9.5.2.3 24-Hour Pain and Urgency Scale Diary and Urination Log

Each subject will be provided with a set of pain and urgency questionnaires that use the 11-point NRSs that will be recorded by the subject at home after receiving the study medication, until going to bed. Pain measurements will be recorded on-site up to 2 hours after study drug administration [at Time 0, 30 minutes (\pm 5 minutes) and 1 hour (\pm 5 minutes), 2 hours (\pm 10 minutes)], and at home at 4 hours (\pm 30 minutes), 6 hours (\pm 30 minutes), 8 hours (\pm 30 minutes), 10 hours (\pm 30 minutes), and 12 hours (\pm 30 minutes) while the subject is awake. The last set of pain and urgency questionnaires will be completed at 24 hours, and may be completed at the clinic if the subject returns to the clinician's office (Visit 2) at 24 hours (\pm 2 hours) after study drug administration or, at the Investigator's discretion, will be completed at home and returned to the clinic per the Investigator's directions. The site staff will ensure that the proper subject initials and numbers, and study drug administration time are recorded in each subject's diary prior to dispensing them. The diary also contains a urination log. The diary will be explained to each subject by the investigator or designee prior to the subject recording any data in the diary. Site staff will be tasked with placing phone calls to remind each subject to complete the diary at the assigned times, and if the subject has been given permission by the Investigator to not return for Visit 2 to confirm the return of the completed subject diary and answer any follow up questions.

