9.7.1.2 Secondary Endpoints

The secondary endpoints of the study are:

1. The sum of bladder pain intensity differences from baseline to 24 hours (SPID-24) after administration of URG101 compared with lidocaine alone, heparin alone, and placebo as determined by using the 11-point bladder pain NRS
2. The sum of urgency intensity differences from baseline to 12 and 24 hours (SUID-12 and SUID-24) after administration of URG101 compared with lidocaine alone, heparin alone, and placebo using the 11-point urgency NRS
3. Absolute and percentage change in bladder pain from baseline to 1, 12, and 24 hours after administration of URG101 compared with lidocaine alone, heparin alone, and placebo as determined by using the 11-point NRS for bladder pain
4. Absolute and percentage change in urgency intensity from baseline to 1, 12, and 24 hours after administration of URG101 compared with lidocaine alone, heparin alone, and placebo using the 11-point urgency NRS
5. Patient Global Assessment: Comparison of the percentage of subjects achieving $\geq 50\%$ improvement in the PORIS questionnaire, Question 3, from baseline to 1 hour, 12 hours and 24 hours after administration of URG101, lidocaine alone, heparin alone, and placebo
6. Time to first administration of rescue medication for pain after treatment with URG101 compared to alkalinized Lidocaine Hydrochloride Injection (20 mg/mL) alone, alkalinized Heparin Sodium Injection (5,000 USPU/mL) alone, and placebo [REDACTED])
7. To evaluate the safety and tolerability of intravesical administration of URG101

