9.7.1.14 Efficacy Analyses

All SPID endpoints will be calculated using Simpson's trapezoidal rule. SPID will be calculated as follows, where n is the total number of time points within the time period with non-missing imputed PID values:

If multiple scores are recorded at the same date and time, the most conservative PI scores (highest) will be used.

Primary Efficacy Analyses

The primary efficacy analyses will be performed on the intent-to-treat set. As a sensitivity analysis, the primary efficacy analysis will also be performed on the PP set. Primary efficacy analyses will also be conducted on the per protocol set, which will include all subjects in the ITT set who sufficiently comply with the protocol.

The primary efficacy endpoint will be compared between the URG101 group and the lidocaine, heparin, and placebo groups using an analysis of covariance model including factors for site and randomized treatment assignment; baseline pain will be added to the model as a covariate. Pairwise comparisons of least squares means between URG 101 and the two active treatment arms, as well as the placebo arm, will be performed. The probability values will be derived using the contrast statement from the model. If the p-value associated with these comparisons is < 0.05 in favor of URG101, the primary aim of the trial will be confirmed.

Sites with small numbers of patients enrolled may be pooled for analysis. The method used to determine pooling will be specified in the statistical analysis plan and any pooling will be finalized and documented prior to database lock and unblinding.

Secondary Efficacy Analyses

Analyses of the secondary endpoints relating to changes in the pain and urgency NRS will be performed using analysis of covariance models similar to those used for the primary efficacy endpoint. The ITT set will be used. Nonparametric methodology in exploratory analyses may be used to supplement the parametric analyses.

Treatment differences based on the PORIS questionnaire, Question 3, will be analyzed by pairwise Cochran-Mantel-Haenszel Tests based on $\geq 50\%$ improvement of symptoms.

Time to first pain medication use will be analyzed using Kaplan-Meier methodolgy. Log-rank tests will be used to compare the treament groups.

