9.7.2 Handling of Missing Data

9.7.2.1 11-Point Bladder Pain and Urgency Scales

For the 11-point numerical data, if subjects are administered any rescue pain medication, the pain score recorded immediately prior to receiving the rescue pain medication will be carried forward for 4 hours. Data for subjects who withdraw will be imputed using the baseline observation carried forward method. The imputed dataset will be used to derive the SPID score.

9.7.2.2 24-Hour Symptom and Urination Diaries

During the 24 hours after treatment, subjects are required to fill in their symptom diaries only while they are awake. Missing data occurring will be imputed using LOCF methodology.

[figure not shown]
If the number of missing data points in the 12-hour period after treatment administration is 6 or greater, then the subject is considered a major protocol violator and his or her data are excluded from the per protocol analysis. If the number of missing data points in the first 6-hour period following treatment administration is 3 or greater, then the subject is considered a major protocol violator and the subject's data are excluded from the per protocol analysis.

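### As written, the synopsis LOCF rule reaches PORIS, so a 1-hour responder with no later rating counts as a responder at 12 and 24 hours

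*Combined protocol and SAP*

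**What the plan says.** - **Missing data, synopsis.** Under Primary Efficacy Determination: "Missing data for efficacy values will be imputed by the last observation carried forward method". No endpoint is excepted, and PORIS is listed under Efficacy in the synopsis evaluation criteria.
- **Missing data, Section 9.7.2.** Section 9.7.2.1, headed for the 11-point scales, uses baseline observation carried forward (BOCF) for subjects who withdraw and feeds the SPID score. Section 9.7.2.2, on the symptom and urination diaries, says "Missing data occurring will be imputed using LOCF methodology". Neither names PORIS.
- **Endpoint, Section 9.7.1.2.** The percentage of subjects with at least 50% "improvement in the PORIS questionnaire, Question 3, from baseline to 1 hour, 12 hours and 24 hours after administration of URG101".
- **Schedule.** Section 9.1.2 has "the PORIS questionnaire at 1 hour" in the clinic. Section 9.1.3 then has "the PORIS questionnaire at 12 hours after study drug administration or before the subject goes to bed for the evening" at home, and tells subjects to "return the next day for the optional 24 hour Follow-up Visit". Section 9.1.4 makes the 24-hour form mandatory even when the visit is skipped.
- **Nature of the rating, Section 9.5.2.2.** "It comprises three questions that ask the subject to report the overall change in pain and urgency" since before dosing. There is no pre-dose PORIS value.
- **Test, Section 9.7.1.14.** "Treatment differences based on the PORIS questionnaire, Question 3, will be analyzed by pairwise Cochran-Mantel-Haenszel Tests".

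**The concern.** With ratings at only three times, a subject who gives no home rating has only the 1-hour value to carry. That value is then reported as response 11 and 23 hours later. The ITT set in Section 9.7.1.5 requires only randomization and dosing, so such subjects stay in the analysis. The exclusions for too many missing points in Section 9.7.2.2 apply only to the per protocol set.

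The plan would also score one subject two ways. Section 9.5.7 allows discontinuation for lack of effect. A subject who responds at 1 hour, relapses and withdraws is set back to baseline on the pain and urgency scales, yet would remain a PORIS responder at 12 and 24 hours. At stake is whether a late PORIS difference shows lasting benefit or partly repeats the 1-hour result.

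**Working it through.** **The plan's own figure.** No figure is given for PORIS or for missingness. The only power statement is for SPID-12 (synopsis: 90% at effect size 0.60 with 60 v 60, and at 0.75 with 60 v 30). A two-sided 0.05 normal approximation gives 90.8% and 91.8%, so it reproduces. It has no bearing on this point.

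**Formulas.** Let m be the fraction with no later rating, equal in both arms and unrelated to response. Let p be an arm's 1-hour response rate and q its true late rate. D1 and DL are the between-arm differences in p and in q.

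- LOCF reports (1 − m)q + mp in each arm. The bias in the difference is m(D1 − DL).
- Scoring missing as non-response reports (1 − m)q. The bias in the difference is −m × DL.

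**Case 1: no true late difference.** Assumed: 1-hour rates 50% v 11%; late rate 11% or 20% in both arms; m = 10% to 30%. The 50% and 11% are borrowed from the URG101-104 results in Section 7.5.1. No rating time is given there, and the 11% is worded as a reduction in symptoms, so both serve only as illustrations. D1 = 39 points and DL = 0. The arms are 60 v 30, as for URG101 v placebo. Rejection rates are exact binomial, using an unstratified pooled z test in place of Cochran-Mantel-Haenszel.

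| m | False late difference, LOCF | Two-sided rejection, LOCF | Difference, non-response | Rejection, non-response |
|---|---|---|---|---|
| 10% | 0.10 × 39 = 3.9 points | 6.5–6.7% | 0 | 4.3–5.1% |
| 20% | 0.20 × 39 = 7.8 points | 12.0–13.6% | 0 | 4.0–5.1% |
| 30% | 0.30 × 39 = 11.7 points | 21.6–25.2% | 0 | 3.7–5.1% |

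With a smaller early gap (50% v 30%, D1 = 20), the false difference is 2, 4 and 6 points.

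**Case 2: a true late difference.** Assumed: URG101 65% at 1 hour and 50% at 12 hours; lidocaine 60% and 30%. D1 = 5 and DL = 20.

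- LOCF, m = 10%: (0.9 × 50 + 0.1 × 65) − (0.9 × 30 + 0.1 × 60) = 51.5 − 33.0 = 18.5 points.
- LOCF, m = 30%: (0.7 × 50 + 0.3 × 65) − (0.7 × 30 + 0.3 × 60) = 54.5 − 39.0 = 15.5 points.
- Non-response, m = 10%: 45 − 27 = 18 points.
- Non-response, m = 30%: 35 − 21 = 14 points.

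Here LOCF is nearer the true 20. For DL > 0, |D1 − DL| < DL whenever D1 lies between 0 and 2 × DL. LOCF therefore gives the smaller error unless the early difference is more than twice the late one, or is reversed.

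**Case 3: unequal missingness.** With a true late rate of 20% in both arms and 10% v 30% missing, non-response scoring gives 0.9 × 20 = 18% v 0.7 × 20 = 14%, a false difference of 4 points.

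**The case against.** **Does LOCF reach PORIS at all?** The synopsis sentence sits under the primary analysis, before PORIS is discussed. Section 9.5.2.3 describes the diary as pain and urgency scales plus a urination log, so the diary rule may not cover PORIS. A figure following that rule in Section 9.7.2.2 is not shown in the available text, and Section 9.7 leaves details to a separate SAP. One could say the PORIS rule is simply unstated. This stands as a limit on certainty. But the synopsis wording is general, PORIS is classed as efficacy, and no other visible rule applies.

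**Will there be much missing?** Diary return and the 24-hour form are mandatory, the second rating may be made at bedtime, and reminder calls are planned (Sections 9.1.3, 9.1.4 and 9.5.2.3). The 10% to 30% range has no source in the documents. This limits the size but does not change the rule.

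**Is the remedy better?** In Case 2 it attenuates more than LOCF does. In one arm with 60% at 1 hour and a true 35% at 12 hours, LOCF reports 37.5% to 42.5% (+2.5 to +7.5 points), while non-response reports 31.5% to 24.5% (−3.5 to −10.5). With equal, random missingness, observed cases would recover the true difference exactly. All of this stands. The remedy rests on protection in Case 1 and on consistency with BOCF.

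**Is it material?** In Case 2 the LOCF shift is 1.5 to 4.5 points, against a standard error of √(0.5 × 0.5/60 + 0.3 × 0.7/60) = 8.8 points. For a real difference of that kind, LOCF does little harm.

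**Conclusion.** The point holds as a defect in the written rule for a secondary endpoint. Read literally, LOCF lets an early PORIS response stand as a late one and conflicts with the return to baseline used for withdrawals on the 11-point scales. If there is no true late difference, the false difference is about 4 to 12 points under assumed 1-hour rates of 50% v 11% and 10% to 30% missing, equally and at random.

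A reader might infer two stronger things that the documents do not support:

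- **A known direction of bias**, such as a smaller difference from lidocaine and a larger one from placebo. The sign is that of D1 − DL, and no PORIS rates by arm and time are given.
- **A 1-hour rating taken near peak effect.** The synopsis calls the 1-hour sample peak plasma lidocaine; no time of peak effect is stated.

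SPID-12 is unaffected.

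**What to change.** In Section 9.7.2 and the synopsis:

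1. Exempt PORIS Question 3 from LOCF. In the ITT set, count a missing 12- or 24-hour rating as non-response at that time, in line with BOCF for withdrawals on the 11-point scales.
2. Add an observed-cases analysis as a sensitivity analysis, and report the number missing by arm and time.
3. Reconcile the blanket LOCF sentence in the synopsis with Section 9.7.2.1.

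This needs only wording and no new data, and should be done before database lock. The cost is that response rates fall in proportion to missingness, a true late difference is attenuated (20 points becomes 18 to 14 at 10% to 30% missing), and unequal missingness can bias the comparison. The sensitivity analysis is there to show how far the result depends on the rule.
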